3. Once eligible volunteering participants have been identified, the research team member will review the informed consent form with the participant (See Appendix B). The form will include information about the study, the time commitment and reimbursement for participation, and how the survey information will be handled. The form will also inform the participant that their participation is confidential and completely voluntary. Additionally, the form will review the minimal risks for participating and PI and SSIRB contact information. They will be instructed to not include any personal identifiers on the survey and other survey materials.
4. If volunteering participants choose to participate in the survey data collection after the consent process, they will be given: a) the Health Beliefs and Behaviors Survey (used in our previous study Protocol 016008; See Attachment) to be completed in the church's fellowship hall or large meeting room at that time (they will be assured of ample room for privacy/confidentiality in completing the survey); and b) an unmarked manila envelope. The first section of the survey instructs participants to create their own study number (secret code) via a series of questions (e.g., first letter of your mother's first name). The survey includes questions regarding: their opinions on African American health screening behaviors (including HIV/STD screening) and preventive behaviors (e.g., exercise, not smoking, healthy eating), HIV/STD health risk behaviors, and beliefs about HIV/STDs. The survey also asks about religious activities, beliefs and knowledge about HIV/STDs, opinions on whether their church should be involved in HIV/STD-related activities and participant exposure to these activities, opinions about drug users and homosexuality, and their demographic information. Participants will also be asked about exposure and satisfaction to their relevant study treatment arm in surveys subsequent to baseline survey(s).
5. Upon completion of the survey, the participants will be asked to place the survey in the envelope and seal it. They will then be asked to place the sealed envelope in a large sealed box to further ensure anonymity. They will then be given the designated and thanked for completing the survey.

Feasibility/Program Evaluation Data Collected from Church Health Liaisons (CHL):

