Intervention Arm. The intervention (Taking It to the Pews; TIPS) will be delivered through church-based multilevel (community, church-wide, ministry group, interpersonal/individual) activities by trained church leaders using religiously/ culturally-tailored study materials (sermon guides, responsive readings, educational games, brochures, educational/testimonials; see Attachments "Materials for Intervention Churches" and "Poster for Intervention Churches") packaged in a TIPS HIV Tool Kit and following a scripted, study implementation manual. Each church will appoint a Health Action Team (two church liaisons and other members) that will deliver study activities and organize HIV testing events with the Kansas City Health Department. Intervention churches will receive the TIPS HIV Tool Kit, including a study manual. These churches will hold a TIPS Kick-off event, where TIPS tools (e.g., a sermon, a responsive reading, an HIV testing video testimonial, two brochures, and a church fan) will be delivered along with the first HIV testing event. After the Kick-off, liaisons will deliver 1-2 Tool Kit materials/activities per month through targeted multilevel church activities; minimum of 24 tools over 12 months. Two additional HIV/STD screening events will be planned and will be open to all persons seeking screening, including study nonparticipants who are interested in free Kansas City Health Department HIV screening. Delivery of intervention components will coincide with existing, multilevel activities that occur in churches through: a) a communitywide outreach ministry events; b) churchwide services, b) inreach/outreach ministry groups; and c) individual level activities over 12 months.

Standard Information Control Arm. Our standard information churches will receive standard multilevel HIV education information similar in type to those provided to the intervention churches. These churches will receive: a) non-tailored project materials (brochures, see Attachment "Materials for Comparison Churches") collected from health organizations and b) standard, non-tailored activities (e.g., community-based HIV testing events) coordinated by their church liaisons. Similar to the intervention churches, control churches will distribute 1-2 nontailored, standard information materials each month. These churches will receive all HIV Tool Kit materials after the completion of 12-month assessments.

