Data will be initially summarized using means, standard deviations, and percentages. Our primary outcome is receipt of HIV testing (tested vs. not-tested) at 12 months. We'll also examine outcomes at 6 months. Churches are the unit of randomization and participants nested in churches will be the level of analysis. Therefore, differences between intervention and standard information groups will be analyzed using random effects logistic regression to account for the clusters and the pairing, or matching, of churches. Multilevel, multivariate models will include fixed-effect terms for experimental condition and potential mediators and moderators, as well as random effect terms for church nested in treatment condition and individual nested within church. This approach has been widely used in other church-based studies. Adjusted odds ratios for HIV testing (and confidence intervals) will be computed for mediators/moderators. Other covariates will be added as indicated by univariate analyses conducted on baseline data. A propensity score matched analysis will also be run using all available covariates. We will use R and SAS statistical software generalized estimating equations and generalized linear mixed modeling for data analyses to determine if there is a difference in HIV screening rates over time between intervention and standard information groups with/without adjusting for covariates. We will do a stratified analysis by Wave to explore differences between: a) Wave 1 intervention and waitlist groups and b) Wave 1 standard information and waitlist groups using similar analysis methods described above. A similar process will also be used to analyze HIV sexual risk behaviors using mixed-model ANOVA programs that allows for adjustment of participant nonindependence within churches.

Specific Aim 2. Evaluate the role of potential mediators and moderators associated with HIV screening behaviors among a church-population at 6 and 12 months.

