Mediation analyses will examine to what extent possible intervention effects on HIV testing might be explained by potential mediators, including TPB-based variables (attitude, normative beliefs, behavioral control, intentions) and other covariates (HIV stigma, HIV knowledge, intervention exposure). We will assess if: 1) intervention is significantly related to outcome (HIV testing); 2) intervention is significantly related to potential mediators; 3) mediators are significantly related to outcome. Specifically, we will estimate the indirect effects defined in terms of products of path coefficients—linking the intervention to outcomes via each potential mediating variable using multilevel structural equation modeling. The statistical significance and precision of these indirect effects will be addressed by: a) employing the product of coefficients approach and b) obtaining bootstrapped confidence intervals for indirect effects. Mediation will be tested using the Sobel test available as a SAS macro and an R package, *bstats*, and by using structural equation models in MPLUS software as described by MacKinnon et al. Effects of potential moderators' ability to modify the strength/direction of the potential causal relationship will be tested using interaction tests in a multifactorial model.

Specific Aim 3. Conduct a process evaluation to understand study implementation facilitators, barriers, fidelity, and costs and examine relationships between study implementation, intervention dose and exposure, and intervention outcomes to identify and improve essential intervention components.

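### SAP Aim 2 treats intervention exposure as a mediator, but its path from arm is set by the design or by the scoring rule, and church attendance can create its path to testing when the tools have no effect

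*SAP*

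**What the plan says.** SAP Specific Aim 2 examines "potential mediators, including TPB-based variables (attitude, normative beliefs, behavioral control, intentions) and other covariates (HIV stigma, HIV knowledge, intervention exposure". The first step asks whether arm is related to testing. The next two are "2) intervention is significantly related to potential mediators; 3) mediators are significantly related to outcome". Indirect effects are products of path coefficients, judged by the Sobel test and bootstrap intervals. The multilevel model under Specific Aim 1 holds "fixed-effect terms for experimental condition and potential mediators and moderators" together with church random effects. On adjustment it says "Other covariates will be added as indicated by univariate analyses conducted on baseline data". Specific Aim 3 is to "examine relationships between study implementation, intervention dose and exposure, and intervention outcomes to identify and improve essential intervention components".

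Protocol section 4a fixes how exposure arises and how it is measured:

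- Data collection: "Participants will also be asked about exposure and satisfaction to their relevant study treatment arm in surveys subsequent to baseline survey(s").
- Intervention Arm: the Kick-off tools (six items are listed as examples) "will be delivered along with the first HIV testing event". After that, 1-2 tools go out each month, at least 24 over 12 months, and two more testing events are planned.
- Standard Information Control Arm: 1-2 non-tailored materials each month. "These churches will receive all HIV Tool Kit materials after the completion of 12-month assessments".
- Church-based HIV/STD testing: three free events at the churches of both arms.

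The survey items are not in the documents, so how exposure will be scored is not known.

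**The concern.** A mediator analysis needs two informative links: arm to mediator, and mediator to outcome given arm. For exposure, the first link carries no information on mechanism. It reflects which materials were sent where, or how two different sets of materials were counted. The second link can arise without any effect of the tools. People who come to church more often see more tools and also have more chances to be tested on site. Arm and church terms do not remove a difference between people in the same church. Nothing requires exposure to come before the test.

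The pilot (Protocol section 3a) already found that greater exposure went with testing. If the trial finds the same, exposure could be reported as the route by which TIPS works, and Aim 3 could name essential components from that link. Churches might then be advised to deliver more tools when more on-site testing was what helped.

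**Working it through.** **Plan's own figures.** The documents give none for mediation. The pilot 12-month rates of 59% and 41% give a difference of 18 points and an odds ratio of (0.59/0.41)/(0.41/0.59) = 2.07, close to the 2.04 reported.

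**Inputs from the Protocol.** 7 churches per arm; 65 participants per church at 12 months, split 70:40 between members and community members (65 × 70/110 ≈ 41 and 65 × 40/110 ≈ 24); at least 24 tools; six Kick-off items; three testing events per arm.

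**Assumptions, not in the documents.** Members attend half of occasions and community members a sixth, with person-to-person spread (beta, concentration 4). Each event attended adds a chance g of being tested, with g = 10%, 20% or 30%. The church coefficient of variation is 0.2 (the Protocol uses one but gives no value). The tools have no effect.

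**Arm to exposure (a).** Mean attendance is (41 × 0.5 + 24 × 0.167)/65 = 0.377.

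- TIPS tools scored: control is zero by design, so a = 24 × 0.377 = 9.05 tools.
- Own-arm materials scored, equal numbers per arm: a = 0.
- Own-arm materials scored, TIPS with six extra Kick-off items: a = 6 × 0.377 = 2.26.

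The scoring rule decides the answer to this step.

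**Exposure to testing (b), TIPS tools scored.** P(test) = 1 - (1 - p0)(1 - g)^(events attended), with p0 set to give 59% or 41%. Exposure = 6 × (Kick-off attended) + binomial(18, attendance), with variance 48.1. Tools do not enter P(test).

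| g | covariance | b = cov/48.1 | a × b (points) | share of 18 points |
|---|---|---|---|---|
| 10% | 0.248 | 0.0052 | 4.7 | 26% |
| 20% | 0.509 | 0.0106 | 9.6 | 53% |
| 30% | 0.779 | 0.0162 | 14.7 | 82% |

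**How often exposure is called a mediator (simulation, 14 churches × 65).**

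| Setting | g = 10% | 20% | 30% |
|---|---|---|---|
| Pilot rates, TIPS tools scored, Sobel | 34% | 88-89% | 100% |
| Same, significant arm effect also required | 30% | 81% | 98% |
| Same, Kick-off items not counted, Sobel | 28% | 80% | 99% |
| Own-arm, TIPS with six extra items, Sobel | 65% | 100% | 100% |
| Own-arm, equal scales, Sobel | about 2-9% across the three | | |
| No arm effect, TIPS tools scored, all three steps | about 3-5% across the three | | |
| No arm effect, TIPS tools scored, Sobel alone | 35-51% | 88% or more | 100% |

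The range in the last row reflects the testing rate assumed common to both arms. If events add nothing (g = 0, pilot rates), Sobel is positive in 4%. At g = 20%, church coefficients of variation of 0.1 and 0.3 give 90% and 89%.

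**A second model.** Here exposure is a continuous score with a 0.5 SD arm gap, and there is a pilot-size arm effect by a non-tool route. Attendance correlates 0.4 with exposure and adds 0.5 log-odds of testing per SD. All three steps are met in 67% of runs (Sobel 65%). With 0.2 and 0.3 instead: 12.5% (12%). With no shared cause: 4.7% (4%). With no arm gap in exposure: 3.4% (2.7%). Adjusting the first case for attendance measured perfectly: 4.5% (4.2%).

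**Time order.** If six Kick-off items count towards the 24, (24 - 6)/24 = 75% of tools come after the first testing event. If they are extra, 24/30 = 80% do. A test taken at the Kick-off is then paired with tools seen later.

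**The case against.** The strongest objection is the SAP's first step. Both arms have three testing events and 1-2 materials a month. If the tools do nothing, an arm effect on testing has no obvious source, and without one the three steps are met together in only about 3% to 5% of runs. A reader might infer that the SAP's steps are met whenever the tools are inert. The documents do not support that. What stands is narrower: TIPS may raise testing by another route, for example better promoted events; and the SAP does not make the Sobel or product test depend on step 1.

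Second, control churches hand out materials at the same monthly rate. On equal own-arm scales the apparent indirect effect is about zero. This stands, and the documents do not say which scoring applies. Even so, a count of brochures against a count of tailored tools does not test mechanism.

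Third, a reader might take all tools to arrive with testing events. Only the Kick-off tools are stated to do so, and some tools go out through individual-level activities. The argument needs only that attendance raises both exposure and access to testing; leaving Kick-off items out lowers the rates little.

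Fourth, the SAP allows baseline covariates and the survey covers religious activities, so attendance could be adjusted for. It could, but the SAP does not commit to it. Nor would baseline attendance remove the Kick-off link: among equally regular attenders, those present that day received tools and a testing opportunity together.

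Fifth, attitude, intention and knowledge also face unmeasured confounding. That is true, but they are not defined by what each arm was sent, so their path from arm can be informative.

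**Conclusion.** The concern holds in a limited form. Intervention exposure is not a usable mediator here, because its path from arm is fixed by design or compares different materials, and its path to testing is open to confounding by attendance with no stated safeguard. If TIPS raises testing by a non-tool route, or if Sobel or product tests are read without step 1, inert tools can be declared the mechanism.

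The size depends heavily on assumptions. It is 34% to 100% with TIPS-tool scoring and event effects of 10% to 30%, about 12% under weaker shared attendance in the second model, and about 2% to 9% on equal own-arm scales. None of these is a forecast for this trial, because attendance, event effects and scoring are not in the documents. Nor should a reader infer that the main result is in doubt: the primary arm comparison, run without mediators, is unaffected.

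**What to change.** In SAP Aims 2 and 3:

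1. Remove intervention exposure from the mediator list and from the multilevel model under Aim 1. Keep the TPB, stigma and knowledge mediators. Report exposure by arm as a delivery check and state how it is scored.
2. Relate exposure to testing within TIPS only, with a church random effect, baseline attendance and member/community status. Report it as an exploratory association with its interval, not as a mediated share. Name no essential component from it alone.
3. Add a lagged sensitivity analysis: exposure reported at 6 months against new testing in months 6-12, among those not tested by 6 months. For Wave 2, count from the second baseline. State that it selects on 6-month testing status and is less precise.

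The cost is about one paragraph. No new data should be needed: testing and exposure are already surveyed at both follow-ups, and the survey covers religious activities, though the items should be checked for a usable attendance measure. Under the assumptions above, the lagged analysis keeps about 270 to 285 of 455 TIPS participants (7 × 65), and fewer if self-created codes fail to link surveys. In that simulation it was falsely positive in 5% to 6% of runs, with attendance measured without error. The 2017 renewal form says the study was not yet in data analysis.

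### Aim 2 does not require a mediator to precede HIV testing, and it does not say which of its mediation tests governs or how each allows for churches

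*SAP*

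**What the plan says.** SAP Specific Aim 2 reads: "Evaluate the role of potential mediators and moderators associated with HIV screening behaviors among a church-population at 6 and 12 months". It names seven candidate mediators: four TPB variables (attitude, norms, control, intentions), HIV stigma, HIV knowledge and intervention exposure. A mediator must pass three conditions: the intervention is related to testing, the intervention is related to the mediator, and "3) mediators are significantly related to outcome". No visit is assigned to mediator or outcome.

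The indirect effects are to be estimated "via each potential mediating variable using multilevel structural equation modeling". Inference is by the product of coefficients and by "obtaining bootstrapped confidence intervals for indirect effects". The next statement is "Mediation will be tested using the Sobel test available as a SAS macro" and in an R package, and also by structural equation models in MPLUS.

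SAP Specific Aim 1 says "Churches are the unit of randomization and participants nested in churches will be the level of analysis". Its models, which may contain mediators, carry "random effect terms for church nested in treatment condition and individual nested within church".

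Three protocol passages bear on timing:
- Section 4(a), Data collection: one survey holds both testing history and beliefs. Wave 1 completes it at baseline, 6 and 12 months. Wave 2 has two baselines, then surveys at 12 and 18 months.
- Section 4(a), Intervention Arm: the first testing event is part of the Kick-off.
- Section 9(e): health department screeners counsel people when they give results.

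**The concern.** There are two separate problems.

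**Time order.** Testing is reported looking back, on the survey that measures beliefs. Someone tested and counselled at the Kick-off first has beliefs re-measured months later. If testing changes knowledge, stigma or intentions, then an intervention that raises testing also moves the belief, and the belief correlates with testing. All three conditions are met although the belief caused nothing.

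**Which test decides.** Several procedures are listed for the same indirect effects. The SAP does not tie the Sobel inputs to the multilevel paths, does not give the bootstrap's resampling unit, and has no rule for conflicting results. The intervention is assigned to 14 churches, so the intervention-to-mediator path has church-level error. Whether each procedure carries that error is left open.

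Aim 2 is meant to explain any intervention effect. A false mechanism would misdirect refinement of the tool kit.

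**Working it through.** **Inputs.** From protocol section 4(a): 14 churches (7 per arm), 110 participants per church at baseline and more than 65 at 12 months, Type I error 5% (two-sided assumed). From section 3(a): pilot 12-month testing of 59% vs 41%. The documents give no mediator ICC and no size for any effect of testing on beliefs, so both are assumed and shown as ranges.

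**1. The plan's own figure.** None is given for mediation. The primary power claim (84% with 10 churches, 91% with 12) rests on a coefficient of variation k that is not stated. It can be back-solved from the unmatched Hayes formula, z = √[(c−1)(p₁−p₀)²/V] − 1.96, with V = p₀(1−p₀)/m + p₁(1−p₁)/m + k²(p₀²+p₁²).
- With m = 65 and k = 0.12, V = 0.00744 + 0.00743 = 0.01488.
- For c = 5 per arm, z = √(4 × 0.0324/0.01488) − 1.96 = 0.99, so power is 84%.
- For c = 6 per arm, z = 1.34, so power is 91%.
- The implied outcome ICC, k²p/(1−p), is 0.010 at 41% and 0.021 at 59%. This is only a rough guide to a mediator ICC.

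**2. Reverse causation.** Assume the mediator has no effect on testing, the intervention moves testing from 41% to 59% (log-OR 0.73), and being tested shifts the mediator by d SD. There are 7 × 65 = 455 people per arm.
- d = 0.5: arm difference 0.18 × 0.5 = 0.090. SD = √(1 + 0.25 × 0.242) = 1.030, so SE = 1.030 × √(2/455) = 0.0683 and z = 1.32. The intervention-to-mediator path is significant in Φ(1.32 − 1.96) = 26% of trials.
- d = 0.8: difference 0.144, SD 1.075, SE 0.0713, z = 2.02, giving 52%.

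Simulated Sobel tests (4,000 runs) agree:

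| Shift d | Ordinary SE, no clustering | Church-level SE, no clustering | Ordinary SE, mediator ICC 0.01 | Church-level SE, mediator ICC 0.01 |
|---|---|---|---|---|
| 0.3 | 8% | 6% | 14% | 5% |
| 0.5 | 23% | 19% | 27% | 12% |
| 0.8 | 52% | 45% | 51% | 29% |

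A separate simulation of the 0.5 and 0.8 cases gave 25% and 49%.

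**3. Sobel on single-level paths (conditional).** The design effect on the intervention-to-mediator path is 1 + 64 × ICC. The actual size of a nominal 5% test is 2[1 − Φ(1.96/√DE)]. The simulation has no intervention effect on the mediator and a real mediator–testing link (log-OR 0.5 per SD, assumed), with churches unpaired.

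| Mediator ICC | Design effect | Path test, formula | Sobel, simulated | With church-level SE |
|---|---|---|---|---|
| 0 | 1 | 5% | 4.0% | 3.8% |
| 0.01 | 1.64 | 12.6% | 10.1% | 3.6% |
| 0.02 | 2.28 | 19.4% | 17.0% | 4.1% |
| 0.05 | 4.20 | 33.9% | 33.1% | 4.2% |

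A stronger link (0.8) gave 11%, 18% and 33%. At 107 per church (1,500/14), the rates are 15%, 26% and 43%. With no mediator–testing link, Sobel is very conservative (0.1% at ICC 0.02).

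**4. Two tempting repairs.**
- Percentile intervals from resampling whole churches, 7 per arm, gave 9.5% to 10.5% false positives on the intervention-to-mediator path. A t reference on 12 df gave 4.7% to 5.5%.
- Pairing a 6-month mediator with testing reported at 12 months is not enough if recall covers 12 months, as in the pilot. If 50% to 70% of tests fall in the first six months and d is 0.5 to 0.8, a null mediator was still significant in roughly 4% to 25% of runs.

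**The case against.** A reader might infer that the plan runs a Sobel test that ignores churches. The documents do not support that. The sentences before it specify a multilevel structural equation model for the indirect effects. Sobel is itself a product-of-coefficients test, so it could take its paths and standard errors from that model. The Aim 1 models that may include mediators also carry a church random effect. Silence in a sentence about software is not a single-level plan. This objection stands, and it makes the rates in step 3 conditional. They also need a real mediator–testing link and an assumed ICC, and they ignore the matching of churches. The 33% belongs to the upper end of the assumed range.

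It can also be said that the shifts in step 2 are assumed, that at 0.3 SD the excess without clustering is small, and that the SAP words Aim 2 cautiously. All of that is fair. None of it answers the time-order point: the multilevel model deals with clustering, not with the direction of cause, and the SAP states no ordering. Nor does it supply a governing test or a resampling unit.

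**Conclusion.** The time-order gap holds as stated. Nothing in either document requires a mediator to precede testing, and the survey and event schedule makes the reverse direction plausible. If testing shifts a belief by 0.5 to 0.8 SD, a belief with no causal role is declared a mediator in about 25% to 50% of trials. At 0.3 SD the rate is 8% without clustering. Church-level standard errors reduce these figures but do not remove the problem at the larger shifts.

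On clustering, the supportable finding is an ambiguity: a Sobel test with no stated cluster adjustment stands beside a multilevel model, with the bootstrap unit unstated and no deciding rule. On the single-level reading, false positives would be about 10% to 18% at ICC 0.01 to 0.02 and 33% at 0.05.

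This is a secondary aim. A reader should not infer any effect on the primary comparison.

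**What to change.** Amend SAP Specific Aim 2 as follows.

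1. Name the multilevel structural equation model as the single governing mediation analysis, with treatment at church level. Build limits for the indirect effect from its paths (for example Monte Carlo limits), with a small-sample reference for the intervention-to-mediator path: t on about 12 df (14 − 2), fewer if the pairing is modelled. Do not rely on a single-level Sobel test or a plain percentile bootstrap of churches.
2. Take the mediator from the 6-month post-start survey. For Wave 2, that is the first survey after its second baseline. Adjust for baseline mediator and baseline testing.
3. State the recall window of the testing item. Restrict the outcome to tests after that mediator survey, with testing already reported there as a covariate, because earlier testing can drive both belief and retesting. If test dates are not recorded, analyse those not yet tested at that survey.
4. Label models that use mediator and testing from the same survey as exploratory.

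The cost is SAP wording. The surveys and software are already planned, and the November 2017 renewal form reports data entry still under way and analysis not begun. The price is wider intervals, loss of early tests from the mediation outcome, and a need to handle missing 6-month surveys. Restricting to those not yet tested also selects on an event after randomisation, so that result should be described as conditional.
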